5.2.15 Treatment emergent adverse event

TEAE is defined as an adverse event occurring (or existing symptoms worsened) on or after the day of first dose intake of study product and up to study end.

5.2.16 Treatment emergent adverse event related to study drug

STATISTICAL ANALYSIS PLAN		
InFlectis BioScience	Sponsor:	InFlectis BioScience
	Protocol Number:	P288ALS
VERSION 1.0 NOV 12, 2024		

TEAE related to study treatment is defined as an event:

- occurring on or after the day of first dose intake of study treatment and up to study end AND
- having a relationship to study treatment equals to “Unlikely”, “Possibly”, “Probably”, “Definitely”, or with a missing relationship.

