2. STUDY OBJECTIVES AND ENDPOINTS

Objectives	Endpoints
Primary	
To assess the safety of the test product, IFB-088 50 mg/day, in patients with bulbar-onset ALS.	
 Incidence, grade and relationship to IFB-088 for treatment emergent AEs, SAEs, and AESIs, AEs leading to dose interruption or premature discontinuation.
Secondary and exploratory	
 Change in ALSFRS-R score from baseline to month 3 and to month 6, Worsening according to ALS-MITOS score, i.e. progression to a higher stage at 3 and at 6 months compared to the baseline, Change in King's College score from baseline to month 3 and to month 6. 
Exploratory endpoints:
 
 Assessment of respiratory function (slow vital capacity [SVC], sniff test [optional], arterial blood gases [ABG]). Evaluation of nutritional status and body composition by bioelectrical impedance.
To determine the PK parameters of IFB-088.	
Measurements of PK parameters:
 
 Plasma concentration of IFB-088 and IFB-139, AUC of IFB-088 and IFB-139, Maximum observed plasma concentration (C_{max}), with associated T_{max}, Terminal or apparent terminal half-life ($t_{1/2}$), Apparent systemic clearance, apparent volume of distribution.

To investigate the effects of IFB-088 on potential biomarkers.	
 Change in TDP-43 plasmatic concentration from baseline to 6 months, compared to placebo, Change in neurofilament (NfL) light chain and NfL heavy chain plasmatic concentration from baseline to 6 months, compared to placebo, Change in plasmatic (neuro)inflammatory biomarkers from baseline to 3 months, and from baseline to 6 months, compared to placebo, Change in plasmatic oxidative stress biomarkers from baseline to 3 months and from baseline to 6 months, compared to placebo.
To investigate the QoL of ALS patients.	Change in ALS assessment questionnaire (ALSAQ-40) from baseline to 6 months.

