7.7 RECORDING OF AN ADVERSE EVENT

The investigator must record all AEs presented or reported by the patient in the AE section of the eCRF. The start date, the actions taken (corrective treatments, dose decrease, temporary or definitive discontinuation of study product, premature withdrawal from the study, none, other) and the outcome (ongoing, recovered with/without sequelae, death) must all be recorded, and the investigator must assess the event in terms of seriousness, severity and relationship to the study products.

When possible, signs and symptoms should be reported as a diagnosis i.e. the investigator should avoid reporting only the signs and symptoms. If there is no medical diagnosis and the signs and symptoms have to be reported, the investigator should record a separate AE for each sign and symptom.

The severity of the AEs will be judged by the investigator(s) and recorded as follows:

- Mild: discomfort noticed but no disruption of normal daily activity,

- Moderate: discomfort sufficient to reduce or affect daily activity,
- Severe: inability to work or perform normal daily activity.

The relationship of the AE to the study product will be judged by the investigator(s) and recorded as follows:

- Not related: a reaction for which sufficient information exists to indicate that the aetiology is unrelated to the study drug; the subject did not receive the study medication or the temporal sequence of the AE onset relative to administration of the study medication is not reasonable or the event is clearly related to other factors (subject's clinical state, therapeutic intervention or concomitant therapy),
- Unlikely: Does not follow a reasonable temporal sequence from administration of the IMP, or is most likely related to another aetiology than the trial drug such as the patient's clinical state, environmental factors or other therapies,
- Possibly: a clinical event, including laboratory test abnormality, with a reasonable time sequence to administration of the drug but which could also be explained by concurrent disease or other drugs or chemicals,
- Probably: a clinical event including laboratory test abnormality, with a reasonable time sequence to administration of the drug, unlikely to be attributed to concurrent disease or other drugs and which follows a clinically reasonable response on withdrawal (de-challenge),

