- Definitely: a reaction that follows a reasonable temporal sequence from administration of the drug, or in which the drug level has been established in body fluids or tissues, that follows a known or expected response pattern to the suspected drug, and that is confirmed by improvement on stopping or reducing the dosage of the drug, and reappearance of the reaction on repeated exposure (re-challenge if applicable).

For safety reporting purpose by the sponsor:

- Reasonable possibility: possibly, probably, definitely related AEs,
- No reasonable possibility: not related, unlikely related AEs.

All AEs and SAEs will be collected from the time of signing of the ICF until participation in study has ended. There is no time limit for investigators for reporting to the sponsor related SAEs they are made aware of.

Adverse events that begin before the start of study intervention but after signing of the ICF will be recorded on the AE eCRF (NTEAEs).

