8.1.5 Efficacy / safety analysis

8.1.5.1 Primary outcome

Usual descriptive statistics will be used and detailed in the SAP to analyse the safety parameters.

AEs will be classified by system organ class and preferred term using the Medical Dictionary for Regulatory Activities (MedDRA). AEs will be listed and summarised by, MedDRA preferred term, severity, and relationship to study drug. In the event of multiple occurrences of the same AE with the same preferred term in one patient, the AE will be counted once as the occurrence.

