5.12.1 Adverse Events

Adverse events will be coded by Primary System Organ Class (SOC) and Preferred Term (PT) using MedDRA dictionary.

5.12.1.1 *Summary of treatment emergent adverse events*

A summary of the number of treatment emergent adverse events, number and percentage of patients with at least one AE will be presented, including:

- AE

STATISTICAL ANALYSIS PLAN		
InFlectis BioScience	Sponsor:	InFlectis BioScience
	Protocol Number:	P288ALS
VERSION 1.0 NOV 12, 2024		

- TEAE
- TEAE related to study drug
- Serious TEAE
- Serious TEAE related to study drug

- Fatal TEAE
- Fatal TEAE related to study drug

- Grade 1 (mild) TEAE
- Grade 2 (moderate) TEAE
- Grade ≥ 3 (severe) TEAE

- Grade ≥ 3 TEAE related to study drug
- Grade ≥ 3 and serious TEAE
- Grade ≥ 3 and serious TEAE related to study drug

- TEAE possibly related to Riluzole

- TEAE leading to temporary discontinuation of study drug
- TEAE leading to definitive discontinuation of study drug
- TEAE leading to premature withdrawal from the study

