5.12.1.2 Treatment emergent adverse events

The number of patients with at least one TEAEs and the corresponding number of events will be described by System Organ Class and Preferred Term overall in the safety population. In case a same patient presented the same AE (i.e. same event as defined according to SOC and PT) several times during the study, only one occurrence will be reported, but the total number of events will be counted. This table will be sorted by decreasing percentage of SOC and PT within SOC for the overall column.

The following listings will be edited in order to complete the AE analyses:

- All TEAE reported along the study
- TEAE related to study drug,
- Serious TEAE,
- Grade ≥ 3 (severe) TEAE,

STATISTICAL ANALYSIS PLAN		
InFlectis BioScience	Sponsor:	InFlectis BioScience
	Protocol Number:	P288ALS
VERSION 1.0 NOV 12, 2024		

- TAESIs

For each listing of AE, the following items will be included: Patient identifier, Country, Age (years), Sex, Start date of treatment - Reported term, MedDRA primary SOC, MedDRA preferred term, Start/end datetime of AE, Seriousness, Seriousness criteria, Relationship to study drug, Intensity, Outcome, Action taken regarding investigational drug, Corrective treatment, and if it is an AE of special interest.

In addition, for specific event of interest, a listing of patients with triglycerides > 5.7 mmol/L with at least 20% increase compared to baseline value will be provided. Triglycerides and Glomerular Filtration Rate will be described by classes defined in section 5.2.

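### SAP 5.2.16 counts adverse events rated Unlikely as related to study drug, against the protocol's only related/unrelated grouping, without declaring or explaining it

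*SAP*

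**What the plan says.** Protocol 7.7 has the investigator rate each adverse event on five levels: Not related, Unlikely, Possibly, Probably, Definitely. It defines Unlikely as an event that "Does not follow a reasonable temporal sequence from administration of the IMP, or is most likely related to another aetiology than the trial drug". It then gives one two-way grouping, introduced by "For safety reporting purpose by the sponsor". Possibly, Probably and Definitely form the reasonable-possibility side. The other side reads "No reasonable possibility: not related, unlikely related AEs".

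Protocol section 2 makes this rating part of the primary endpoint: "Incidence, grade and relationship to IFB-088 for treatment emergent AEs, SAEs, and AESIs". For the analysis, protocol 8.1.5.1 says that "AEs will be listed and summarised by, MedDRA preferred term, severity, and relationship to study drug". It sets no two-way split there and leaves the detail to the SAP.

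SAP 5.2.16 supplies a split. A TEAE counts as related if it starts on or after the first dose and up to study end, "having a relationship to study treatment equals to “Unlikely”, “Possibly”, “Probably”, “Definitely”, or with a missing relationship". The definition feeds five rows of the TEAE summary in SAP 5.12.1.1 (for example "Serious TEAE related to study drug") and the listing of related TEAEs in 5.12.1.2. The main event table is "described by System Organ Class and Preferred Term overall in the safety population" and is not broken down by relationship. SAP section 7 lists two changes from the protocol: the ALSFRS-R model with its imputation, and the removal of the Bayesian analysis. Causality grouping is not among them.

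**The concern.** The same investigator rating falls on different sides in the two documents. An event that the investigator judged to have no plausible timing, or most probably another cause, would be tabulated as related to study drug. Protocol 7.10 has ALS complications recorded as adverse events, and this is a fatal disease, so the situation is realistic. A death rated Unlikely would sit under no reasonable possibility for sponsor reporting and also appear in the SAP's row of fatal related TEAEs.

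The rule applies to both arms, so it can add background events to the placebo count as well as to the IFB-088 count and blur the comparison. No other planned summary table described in the SAP shows relationship to study drug. A reader of the related rows could not tell how much comes from Unlikely events without recounting from the listings.

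**Working it through.** The plan states no figure on this point, so there is none to reproduce. The check is a comparison of texts, followed by an illustration of size.

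**Step 1. Placement of each rating**

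| Rating | Protocol 7.7 | SAP 5.2.16 |
|---|---|---|
| Not related | unrelated | unrelated |
| Unlikely | unrelated | **related** |
| Possibly | related | related |
| Probably | related | related |
| Definitely | related | related |
| Missing | not addressed | related |

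Only Unlikely changes sides. The protocol contains no other two-way grouping. Its SUSAR definition (7.6) uses the same reasonable-possibility idea.

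**Step 2. Outputs affected.** These are the five rows of SAP 5.12.1.1 for related TEAEs (all; serious; fatal; grade ≥ 3; grade ≥ 3 and serious) and the related listing in 5.12.1.2. The all-cause rows, the SOC/PT table and the other listings do not use the definition.

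**Step 3. Direction.** A patient-level count rises only when a patient has an Unlikely event and no event rated Possibly or higher in that row. Each count is therefore equal to or higher than under the protocol grouping, and a sparse row may not change at all.

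**Step 4. Size, under assumed rates.** The documents give no frequencies by rating. Assume that a proportion r of patients has at least one event rated Possibly or higher (r = 0.30 on IFB-088, 0.10 on placebo), and that the same proportion q in each arm has at least one Unlikely event. Under the protocol grouping the difference is 20 points and the ratio 3.0. Expected counts use the planned 28 and 14 evaluable patients: 28 × 0.30 = 8.4 and 14 × 0.10 = 1.4.

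If the two kinds of event are independent within patients, the SAP rate is 1 − (1 − r)(1 − q):

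| q | IFB-088 | Placebo | Difference | Ratio | Expected counts |
|---|---|---|---|---|---|
| 10% | 1 − 0.7 × 0.9 = 37% | 1 − 0.9 × 0.9 = 19% | 18 points | 1.95 | 10.4 v 2.7 |
| 20% | 1 − 0.7 × 0.8 = 44% | 1 − 0.9 × 0.8 = 28% | 16 points | 1.57 | 12.3 v 3.9 |
| 40% | 1 − 0.7 × 0.6 = 58% | 1 − 0.9 × 0.6 = 46% | 12 points | 1.26 | 16.2 v 6.4 |

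Overlap within patients sets the bounds:

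| q | No overlap, r + q | Difference; ratio | Maximum overlap, max(r, q) | Difference; ratio |
|---|---|---|---|---|
| 10% | 40% v 20% | 20 points; 2.0 | 30% v 10% | 20 points; 3.0 |
| 20% | 50% v 30% | 20 points; 1.67 | 30% v 20% | 10 points; 1.5 |
| 40% | 70% v 50% | 20 points; 1.40 | 40% v 40% | 0 points; 1.0 |

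**Step 5. Unequal q.** If Unlikely events were commoner on IFB-088, the difference could widen. With q = 20% v 10% and independence, the rates are 44% v 19%. The difference is then 25 points (up from 20) and the ratio 0.44/0.19 = 2.3 (down from 3.0).

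**The case against.** The strongest reply is that no protocol analysis rule is broken. The grouping in 7.7 is written for safety reporting, and 8.1.5.1 leaves the safety descriptives to the SAP, so the SAP was free to choose a split. On that reading there was no planned dichotomy to list as changed in section 7. This stands as far as it goes: the fault is an unexplained inconsistency between the documents, not a violation.

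The rule also fits a cautious pattern. The SAP counts missing relationship as related and missing seriousness as serious, and it dates an AE with no start date to the first dose. Unlikely leaves more doubt than Not related, and the wider definition cannot understate related counts. That is a defensible convention, but the SAP does not state it. Caution explains the handling of missing ratings better than it explains regrouping a rating that was actually given.

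Further points also stand. The rows are descriptive and no test is applied to them. Every AE listing carries the recorded relationship, so with 50 patients planned the protocol grouping can be rebuilt. Dilution is not certain, because unequal rates of Unlikely events could widen the difference. The related rows use the Safety Set, which would be nearer 33 v 17 if all 50 patients are dosed at 2:1 (50 × 2/3 and 50 × 1/3); that changes the expected counts but not the rates. The table shells, which are not available here, might contain a fuller display, although the SAP text describes none. These points limit the importance of the issue. They do not remove it, because a component of the primary endpoint should not need a recount by hand.

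**Conclusion.** The concern holds. SAP 5.2.16 moves Unlikely to the related side, against the protocol's only grouping and against the protocol's own definition of the term, and gives no reason. Five summary rows and one listing are affected, and these are the only summary of relationship to study drug that the SAP describes. Counts in them can be inflated in both arms but never reduced.

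The effect on the contrast between arms depends on rates the documents do not give. Under the assumed 30% v 10% with equal q of 10% to 40%, the difference ends between 20 and 0 points and the ratio between 3.0 and 1.0, depending on overlap within patients. With independence the ratio is 1.95 to 1.26. The finding itself rests on the text and not on these figures. It should be corrected, but it does not threaten the all-cause safety results.

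**What to change.** In SAP 5.2.16, define related as Possibly, Probably, Definitely or missing, and treat Unlikely and Not related as not related, in line with protocol 7.7. If the wider definition is wanted as a cautious view, present it as a labelled sensitivity table and declare it, with its reason, in section 7. In either case add one table of TEAEs by the five relationship levels and arm, which delivers the summary by relationship that protocol 8.1.5.1 asks for and lets readers apply either grouping.

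The cost is one line in 5.2.16, one line in section 7 if the wider view is kept, and one extra table. No data change is needed. The change should be made before unblinding; if the database is already locked, SAP section 5 provides for a documented addendum.

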5.2.17 Non-treatment emergent adverse event

Non-treatment emergent adverse event corresponds to AE that occurs before the study intervention administration (and not worsen). An AE that will not qualify as a TEAE will be considered as a Non-Treatment Emergent Adverse Event (Non-TEAE).

5.2.18 Serious adverse event

SAE corresponds to AE considered as serious or AE with a missing or unknown seriousness. Seriousness of AE will be analyzed according to the investigator judgement.

5.2.19 Adverse event of special interest

The following adverse events will be considered as AESIs (as per study protocol):

- Renal toxicities.
- Symptomatic hypotension grade 2 (requiring non-urgent medical intervention) or above according to common terminology criteria for adverse events (CTCAE) version 5.0.
- Hypertriglyceridaemia: A cut-off value is set at triglycerides > 5.7 mmol/L (5.0 g/L) with at least 20% increase compared to baseline value.

The AESIs will be evaluated using the safety data collected during the study, no specific identification of AESI using pre-defined MedDRA preferred term code will be formally performed on the AE data. Of note, the preferred term code “10021097” (preferred term=“Hypotension”) and “10020869” (preferred term=“Hypertriglyceridaemia”) could be used to identify those AESIs from the AE summary. For the triglycerides parameter, a specific check of the result could also be performed using the quantitative results to identify potential HTG.

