7.4 DEFINITION OF AN ADVERSE EVENT OF SPECIAL INTEREST

An AESI (serious or non-serious) is an AE of scientific and medical concern specific to the sponsor's product or program, for which ongoing monitoring and rapid communication by the investigator to the sponsor can be appropriate.

The following will be considered as AESIs:

- Renal toxicities,
- Symptomatic hypotension grade 2 (requiring non-urgent medical intervention) or above according to common terminology criteria for adverse events (CTCAE) version 5.0,
- Hypertriglyceridaemia (HTG). A cut-off value is set at triglycerides > 5.7 mmol/L (5.0 g/L) with at least 20% increase compared to baseline value.

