8. STATISTICS

8.1 STATISTICAL AND ANALYTICAL METHODS

8.1.1 General statistical considerations

Statistical analyses will be performed by the sponsor or under the supervision of the sponsor and further detailed in the SAP, which will be finalised prior to the unblinding of data and database lock.

In general, summary tabulations will be presented by treatment arm and will display the number of observations, mean, standard deviation (SD), median, Q1, Q3 quartiles, minimum, and maximum for continuous variables, and the number and percent per category for categorical data.

Patient disposition

An accounting of study patients by disposition will be tabulated and the number of patients in each analysis set will be summarised. Patients who discontinue study treatment and patients who withdraw from the study, with associated reason(s), will be summarised. A summary of protocol deviations by treatment arm and the corresponding listing by patient will be generated.

Nominal alpha level of significance

Unless otherwise noted, as the trial is a safety trial and an estimation efficacy study and not powered for efficacy endpoints, all tests performed on efficacy assessments will be conducted at a 1-sided nominal alpha level of 0.10 and confidence intervals (CIs) will be calculated at 80%, 2-sided 95% confidence intervals will also be provided.

Missing data handling

As a general rule, missing data will not be replaced. Sensitivity analyses based on multiple imputation will be proposed and further detailed in the SAP.

Multiplicity

As it is mainly an estimation trial, there is no adjustment for multiplicity.

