2.2 Endpoints

2.2.1 Safety Endpoints

- Adverse Event (AE) and Treatment Emergent Adverse Event (TEAE)
- Laboratories parameters
- Vital signs
- ECG parameters

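### AESIs are part of the primary endpoint, but the SAP gives them only in listings, with no tabulated incidence by arm and no complete identification rule

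*SAP*

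**What the plan says.** Protocol section 2 defines the first primary endpoint as "Incidence, grade and relationship to IFB-088 for treatment emergent AEs, SAEs, and AESIs". Protocol 8.1.1 sets the display rule: "In general, summary tabulations will be presented by treatment arm", with number and percent for categorical data.

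Protocol 7.4 names three AESIs, and SAP 5.2.19 repeats them:
- renal toxicities, with nothing further;
- "Symptomatic hypotension grade 2 (requiring non-urgent medical intervention) or above according to common terminology criteria for adverse events (CTCAE) version 5.0";
- hypertriglyceridaemia, defined by triglycerides above 5.7 mmol/L and a rise of at least 20% over baseline.

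SAP 5.2.19 then states that "no specific identification of AESI using pre-defined MedDRA preferred term code will be formally performed on the AE data". It adds that the preferred terms Hypotension and Hypertriglyceridaemia "could be used to identify those AESIs from the AE summary", and that quantitative triglyceride results could also be checked.

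For outputs, SAP 5.12.1.1 lists the rows of the adverse-event summary. They cover all AEs, TEAEs, related, serious, fatal, graded and riluzole-related events, and those leading to discontinuation or withdrawal. No row is for AESIs. SAP 5.12.1.2 has an AESI listing, requires each AE listing to show "if it is an AE of special interest", and adds that "a listing of patients with triglycerides > 5.7 mmol/L with at least 20% increase compared to baseline value will be provided". AESIs are also absent from the safety endpoints in SAP 2.2.1. SAP section 7 declares two changes to the protocol analysis, both about efficacy.

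**The concern.** A listing shows individual events. It does not state an incidence, and it does not summarise grade or relationship by arm. As written, the plan produces no tabulated result for a component that the protocol puts in the primary endpoint, and it does not say that this was intended.

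The identification rule matters because these events were chosen for specific reasons. Protocol 1.3 makes renal toxicities AESIs in response to crystal nephropathy in rats. The same section gives the expected absence of hypotensive effects as the advantage of IFB-088 over guanabenz. If the way of counting these events is settled after the treatment codes are known, a small number of judgement calls could change how the arms compare.

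**Working it through.** **1. The plan's own safety figure.** The only calculation tied to the primary safety endpoint concerns SAEs (Protocol 8.1.2, SAP section 3). With n = 28, the probability of at least one event is 1 − (1 − p)^28:
- p = 0.05: 1 − 0.95^28 = 76.2%, as stated;
- p = 0.10: 1 − 0.90^28 = 94.8%, as stated.

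The inflation for drop-out also agrees: 42 / (1 − 0.15) = 49.4, rounded up to 50. There is no numerical error. The question is about planned outputs.

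**2. Endpoint against outputs.** The endpoint names three event types (TEAEs, SAEs, AESIs) and three attributes (incidence, grade, relationship). SAP 5.12.1.1 has rows for TEAEs and for serious TEAEs, including related and grade 3 or above. For AESIs it has none. The table by system organ class and preferred term (SAP 5.12.1.2) does not group AESIs either, and its wording refers to an overall display.

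**3. Definition against the note in SAP 5.2.19.**

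| AESI | Conditions in Protocol 7.4 | What the note supplies | Gap |
|---|---|---|---|
| Hypotension | Symptomatic; CTCAE v5.0 grade 2 or above | One preferred term | Carries neither condition |
| Hypertriglyceridaemia | Above 5.7 mmol/L; rise of at least 20% | One preferred term and an optional laboratory check | Closed only if the check is made |
| Renal toxicities | No term list or threshold | Nothing | No rule |

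**4. Can recorded severity repair the hypotension row?** No. Protocol 7.7 records severity as mild, moderate or severe by effect on daily activity, and SAP 5.12.1.1 relabels these as grades 1, 2 and 3 or above. The grade 2 condition in the AESI definition turns on a non-urgent medical intervention. A hypotensive event that was treated but did not disrupt daily activity would be recorded as mild. One that limited activity without treatment would be recorded as moderate. Filtering the preferred term by recorded severity therefore does not recover the definition.

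**5. What an AESI row would report.** Assumed event counts, with exact (Clopper-Pearson) 95% intervals, at the planned 28 and 14:
- IFB-088: 0/28 = 0% (0 to 12.3%); 1/28 = 3.6% (0.1 to 18.3%); 3/28 = 10.7% (2.3 to 28.2%);
- placebo: 0/14 = 0% (0 to 23.2%); 1/14 = 7.1% (0.2 to 33.9%).

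If all 50 are treated and split about 33 to 17 (an assumption), one patient is 1/33 = 3.0 or 1/17 = 5.9 percentage points.

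**The case against.** The best defence is that the information is all there.
- Investigators must report every AESI within 24 hours on a dedicated form (Protocol 7.9), and the AE listings show the designation.
- The triglyceride listing in SAP 5.12.1.2 is a commitment and applies the exact rule.
- Listings are sorted by treatment group first (SAP 5.3), so with about 50 patients a by-arm count can be read off.
- Safety analyses are by treatment received (SAP 5.12). Triglyceride and GFR classes, laboratory shift tables and blood pressure by visit and group are also planned.
- The table shells are a separate document (SAP section 5) and might contain an AESI row.

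All of this is correct, and it rules out some stronger readings. A reader might infer that the two preferred terms are the SAP's counting method, or that renal AESIs cannot be counted at all. The documents do not support either: the note is optional, and renal events that investigators designate will appear in the listing. A reader might also infer a known degree of over-counting from the gap between the SAP's normal limit for triglycerides (1.71 mmol/L) and the AESI cut-off (5.7 mmol/L). That compares two thresholds, not event counts, and Protocol 4.2.1.1 makes a laboratory value an AE only when the investigator judges it clinically significant. For hypotension the documents give no data on how many events would qualify. A single-term count could also miss events coded to another term, so even the direction is open.

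The defence does not supply a planned result. Reading counts off a listing is an unplanned hand count after unblinding. The related displays do not apply the AESI definitions; the triglyceride classes, for example, ignore the 20% rise. A row in the shells, which are not among the documents, would still need the identification rule that the SAP leaves open.

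**Conclusion.** The point holds as a gap in reporting and derivation. One of the three event types in the primary endpoint has no planned by-arm table for any of its three attributes, and the omission is not declared. Of the three AESI categories, only hypertriglyceridaemia has an exact rule that the SAP commits to applying, and that is for a listing. Hypotension rests on the investigator's designation, beside an optional term that does not match the definition. Renal toxicities rest on the designation alone.

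No endpoint, test or data collection is affected, and no bias in a particular direction can be shown. The practical size is the weight of one patient: 3.6 percentage points in 28 and 7.1 in 14, or about 3 and 6 if 33 and 17 are treated. This assumes that the SAP text is the full specification and that the designation shown in the listings is held as a data field.

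**What to change.** In SAP 5.12.1.1, add rows by treatment received for the number and percentage of patients with any treatment-emergent AESI and with each of renal toxicity, symptomatic hypotension and hypertriglyceridaemia. Show recorded severity and relationship for each.

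In SAP 5.2.19, state the identification rule:
- use the investigator's AESI designation, as reported under Protocol 7.9 and shown in the SAP 5.12.1.2 listings, after confirming which data field holds it;
- count hypertriglyceridaemia also by the laboratory rule already used for the triglyceride listing, and list any patient on whom the two disagree;
- fix a term list for renal toxicities before unblinding, with content for the sponsor's medical team to settle;
- remove the two preferred terms as a means of identification.

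The cost is SAP wording and a few table rows. No new data are needed. If the database is already locked, SAP section 5 provides for a documented addendum.
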